## **6.2 Statistical Methods**

Descriptive statistics will be used to characterize the data distribution with normally distributed data presented as means and standard deviation, otherwise median and interquartile range will be used. Proportions will be presented in numbers and percentages. All data analyses will be performed using a statistical tool (SPSS, version 15.0, SPSS). Mann-Whitney U test or Student's t-test and Kruskal-Wallis or ANOVA test will be used depending on the data distribution and the number of variables. All statistical analyses will use a  $p < 0.05$  as statistically significant. Any additional statistical analyses will be determined during secondary data analysis with help from a statistician.

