### 2.1 Primary Objective

To evaluate Hi-VNI use for airway management and oxygenation in upper airway surgery from the anesthesiologist's and the surgeon's perspective with the specific focus on:

CONFIDENTIAL

This material is the property of the University of Pennsylvania.

- Physiologic changes during Hi-VNI use in apneic and spontaneously breathing patients such as maintenance of SpO2, changes in TcpCO2 (transcutaneous CO2) levels, and changes in vital signs, namely heart rate and blood pressure.

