### **3.2 Allocation to Interventional Group**

All subjects included in this study will undergo the same intervention, defined as the use of Hi-VNI as primary or adjunct oxygenation technique.

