### Schedule of events:

### 3.4 Study Endpoints

#### 3.4.1 Primary Study Endpoint

The primary endpoint for this study will be case completion rate without alternative mode of oxygenation. In other words, for each case, the ability to complete the surgical procedure with use of only Hi-VNI device for oxygenation will be assessed.

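### Section 6.2 names a family of between-group tests linked to no endpoint, with no explicitly paired method for within-patient change and no interval or categorical method for the yes/no primary endpoint

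*Combined protocol and SAP*

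**What the plan says.** - **Tests.** Section 6.2 states that "Mann-Whitney U test or Student's t-test and Kruskal-Wallis or ANOVA test will be used depending on the data distribution and the number of variables", with significance at p < 0.05. The Statistical Methodology row of the Study Summary carries the same sentence. Neither place says which outcome is tested, between which groups, or at which times.
- **Proportions.** Section 6.2 adds that "Proportions will be presented in numbers and percentages". It names no confidence interval and no test for them.
- **Anything else.** "Any additional statistical analyses will be determined during secondary data analysis with help from a statistician".
- **Design.** Section 3.2: "All subjects included in this study will undergo the same intervention". Section 6.1 confirms that there is no comparison or control group.
- **Primary objective.** Section 2.1 focuses on "Physiologic changes during Hi-VNI use in apneic and spontaneously breathing patients", listing SpO2, TcpCO2, heart rate and blood pressure.
- **Primary endpoint.** Section 3.4.1: "The primary endpoint for this study will be case completion rate without alternative mode of oxygenation". This is one yes/no value per case.
- **Primary analysis.** Section 6.3.2 plans means and standard deviations for the primary outcomes.
- **Secondary endpoints.** Section 3.4.2 lists total case duration, time to emergence, nadir SpO2, peak TcpCO2 and rate of change in TcpCO2. Each is one number per patient.

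**The concern.** The tests named do not match the two quantities the study is chiefly about.

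The first is change during Hi-VNI, which compares a patient with himself or herself. Mann-Whitney and Kruskal-Wallis compare different patients. Student's t and ANOVA have paired and repeated-measures forms, but here they appear as the normal-theory partners of those two rank tests, which points to the two-sample and one-way forms. Had paired analysis been meant, the rank partners would be Wilcoxon signed-rank and Friedman, and neither is named. For non-normal data the plan therefore has no paired option at all.

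The second is a binary endpoint. The objectives include describing the patients and pathologies for which Hi-VNI suits, and section 3.1 bases this on cases completed without an adjunct technique. Modelling completion by pathology or patient type needs a categorical method, and none is named. Means and standard deviations (section 6.3.2) do not suit a yes/no outcome.

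The selection rule is also loose. The number of groups, and whether the readings are paired, decide between these tests; the number of variables does not.

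At stake are modest changes in heart rate, blood pressure or SpO2 that an unpaired test could miss, and a primary result published without the interval that the sample size was built to deliver.

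**Working it through.** **1. What the sample size rests on.** Section 6.1 gives a 16% completion rate, 95% confidence, a 5-point margin, 144 qualifying cases a year and n = 86.

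- One-proportion formula: n0 = 1.96² × 0.16 × 0.84 / 0.05² = 206.5. This alone does not give 86.
- With a finite-population correction to 144: 206.5 / (1 + 205.5/144) = 85.08, rounded up to 86. This reproduces the plan's figure, and 86 + 14 = 100.

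So the study was sized to estimate one proportion with a 95% interval. None of the four named tests produces that interval, and sections 6.2 and 6.3.2 do not plan it.

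**2. What that interval would look like.** Exact (Clopper-Pearson) 95% limits at the plan's expected rate:

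- 16/100: 9.4% to 24.7%.
- 14/86: 9.2% to 25.8%.

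These treat the patients as a sample from a larger population. The simple normal half-width at n = 100 is 1.96 × √(0.16 × 0.84/100) = 7.2 points, or 4.0 points if 144 cases are taken as the whole population.

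**3. Mean and SD of a yes/no endpoint.** Coded 0/1, the mean is the completion rate itself. The SD is √(p(1 − p)), which at p = 0.16 is 0.367. It is fixed by the rate and adds nothing; it is not a measure of precision.

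**4. Which quantities the named tests fit.**

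- Nadir SpO2, peak TcpCO2, TcpCO2 slope, durations, age or BMI, compared between different patients (for example completers and non-completers): they fit.
- Before versus during readings on the same patients: Mann-Whitney and Kruskal-Wallis do not fit; t and ANOVA fit only in paired or repeated-measures form, which is not stated.
- The overall completion rate, or completion as the outcome by pathology group: they do not fit.

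**5. Size of the error if paired readings were tested as unpaired.** The within-patient correlation r is not in the documents. I assume a range of 0 to 0.7, with equal variances σ² and n patients.

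- Paired SE = √(2σ²(1 − r)/n). Unpaired SE = √(2σ²/n). Ratio = 1/√(1 − r).
- True type I error of a nominal 5% unpaired test = 2 × (1 − Φ(1.96 × ratio)).

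| assumed r | SE ratio | true type I error, formula | simulated t (100 pairs, 4,000 runs) |
|---|---|---|---|
| 0 | 1.00 | 5.0% | 5.1% |
| 0.3 | 1.20 | 1.9% | 2.0% |
| 0.5 | 1.41 | 0.6% | 0.5% |
| 0.7 | 1.83 | 0.03% | 0.1% |

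Mann-Whitney behaved almost identically in the simulation, and the paired t-test stayed near 5% throughout. With positive correlation the error is conservative: too few significant findings, not too many.

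**6. Where it would matter.** For TcpCO2, hardly at all. Section 6.1 expects a rise of 20.25 to 30.38 mmHg. With an assumed SD of 10 mmHg per reading and n = 100, even the unpaired SE is √(2 × 10²/100) = 1.4 mmHg. Smaller changes in heart rate, blood pressure or SpO2 are the ones that could be missed.

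**The case against.** The strongest reply is that section 6.2 is silent rather than wrong. It assigns no test to any endpoint, so nothing instructs an analyst to run an unpaired test on paired readings. Student's t and ANOVA can be paired or repeated-measures. Proportions are at least to be reported as counts and percentages, so the primary endpoint does have a summary. Completion can serve as the grouping variable: comparing age or BMI between completers and non-completers by t or Mann-Whitney is valid and serves the aim of describing the ideal patient. This is a single-arm pilot without a power calculation, and further analyses are left to be settled with a statistician.

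All of that stands, and it limits the point. It does not dispose of it. The plan states a test family that has no paired option for non-normal data and no categorical method, and leaving other analyses until later specifies nothing for the primary endpoint.

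Two stronger readings are tempting and should not be drawn.

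- *That the planned tests will give wrong standard errors.* That follows only if an unpaired test is applied to paired readings, which the plan does not prescribe.
- *That standard errors will be too small because the many readings from continuous monitoring are treated as independent.* The documents nowhere propose such pooling. The physiologic endpoints in section 3.4.2 are one number per patient, and any figure would need an invented number of readings and an invented intraclass correlation.

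**Conclusion.** The concern holds as a mismatch between the stated test family and what the study sets out to measure, of moderate severity. Section 6.2 does not link tests to endpoints, names no explicitly paired or repeated-measures method and no categorical method, and omits the confidence interval that justified the sample size. Section 6.3.2 does not fill the gap for a binary endpoint.

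The size of the pairing error, 1.20 to 1.83 times on the standard error, is conditional on an unpaired test being used, on an assumed r of 0.3 to 0.7 and on equal variances; at r = 0 there is none. The absence of the completion-rate interval rests on no assumption; it can be read directly from sections 6.1, 6.2 and 6.3.2. The documents do not support a claim that the analyses as planned are invalid, and the named tests keep a legitimate use between independent patient groups.

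**What to change.** Reword section 6.2 and align section 6.3.2 and the Study Summary:

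1. **Primary endpoint.** Report the Hi-VNI-only completion rate with an exact (Clopper-Pearson) 95% confidence interval, in place of a mean and SD.
2. **Within-patient change.** For SpO2, TcpCO2, heart rate and blood pressure, report change from the last reading before Hi-VNI starts, with a 95% confidence interval, by paired t-test or Wilcoxon signed-rank test. If several readings per patient are used, fit a mixed model with a patient random effect.
3. **Completion by patient or pathology group.** Use Fisher's exact test or logistic regression.
4. **The tests now named.** Keep them only for continuous measures compared between independent groups of patients. Name the groups, and choose the test by distribution and number of groups.

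The cost is SAP wording only. This point needs no new data and no change to the sample size.

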## 2 Study Objectives

The overall objectives for this study are to establish the efficacy of Hi-VNI in upper airway surgery from the anesthesiologist's and surgeon's perspectives, and to describe the ideal patient and the ideal pathology as well as suitable clinical scenarios when this oxygenation technique should be selected. This study will not change labeling of the Hi-VNI Precision Flow device by the Vapotherm and is not intended to change marketing claims of the manufacturer pertaining to this device.

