## **6 Statistical Plan**

### **6.1 Sample Size and Power Determination**

The subjects will be recruited prospectively based on the eligibility criteria for this study. The investigators anticipate that 100 subjects will be recruited for this study between January 2020 and January 2021. This sample size is determined based on the previously noted caseload for our practice and the fact that this study duration will be limited to one year only. No comparison or control group will be used for this study. The calculation of statistical power will not be required. Patel et al showed that a rate of rise in pCO2 was 0.15 kPa/min with Hi-VNI oxygenation while measuring end tidal CO2 transcutaneously, which translates into 1.125 mmHg/min. Another study by Gustaffson et al cited average apnea duration during elective

laryngeal surgery of  $22.5 \pm 4.5$  min. Based on these values of the rate of rise for pCO2 and the average apnea duration for elective laryngeal surgery, assuming normal data distribution, the range of TcpCO2 change for procedure length within one standard deviation of the mean value (22.5 min) will be [20.25; 30.38].

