Using a normal end-tidal CO2 value of 37.5 mmHg and adding this value to the limits of the range of change in TcpCO2 listed above will give us a range of the values for TcpCO2 at the end of the procedure assuming the average duration of the procedure is  $22.5 \pm 4.5$  min. This range of the TcpCO2 at the end of the procedure would be [57.75; 67.88]. Our cutoff of TcpCO2 minus the baseline gradient between TcpCO2 and end-tidal CO2  $> 55$  mmHg is when the mode of oxygenation will be changed from Hi-VNI to an alternate method (endotracheal intubation or HFJV). The baseline gradient will be measured as the TcpCO2 minus the end-tidal CO2 during routine pre-oxygenation with a facemask. Based on the normal distribution assumption, one can deduce that only procedures with the duration one standard deviation away from the mean duration value of 22.5 min will not reach this level of TcpCO2. In other words, approximately 16% of patients will not require alternate means of ventilation (population which falls to the left of the line through a value of (22.5-4.5) on the normal distribution curve or 15.85%). Based on the author's prior experience and operative volume, there are 2-3 elective cases per week performed by the PIs that may qualify based on the inclusion/exclusion criteria to be included in the study. If 3 cases per week is used will equal to 144 qualified cases per year. For the confidence interval of 95% and the margin of error of 5% with the rate of 16%, the calculated sample size will equal to 86 individuals who might have a good chance of having their procedure completed with Hi-VNI without a need to switch to alternate mode of oxygenation. To account for the fact that some patients may not consent to be in the study or may require alternate means of oxygenation after Hi-VNI is used for other reasons, we added 14 patients to the sample size. This would lead to an estimated sample size of 100 individuals.

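### The 86 in Section 6.1 is a total to enrol, not a count of likely completers; with few completers implied and p < 0.05 applied to every analysis, any ideal-patient comparison risks chance or exaggerated findings

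*Combined protocol and SAP*

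**What the plan says.** Section 2 sets out "to describe the ideal patient and the ideal pathology as well as suitable clinical scenarios when this oxygenation technique should be selected". Section 3.1 draws the optimal scenarios from cases completed on Hi-VNI alone, and Section 3.4.1 makes that completion rate the primary endpoint. Section 3.3 records age, sex, weight, height and BMI, plus other history that it does not list.

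Section 6.1 states "No comparison or control group will be used for this study" and "The calculation of statistical power will not be required". It derives a completion rate ("approximately 16% of patients will not require alternate means of ventilation"), calculates 86 from it, and describes those 86 as "86 individuals who might have a good chance of having their procedure completed with Hi-VNI without a need to switch". It then adds 14 to reach 100.

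Section 6.2 starts with descriptive statistics, then lists t or Mann-Whitney and ANOVA or Kruskal-Wallis tests without naming groups or variables. It states "All statistical analyses will use a $p < 0.05$ as statistically significant" and closes with "Any additional statistical analyses will be determined during secondary data analysis with help from a statistician".

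**The concern.** Two things combine. First, a reader of Section 6.1 could believe that some 86 patients are expected to complete on Hi-VNI alone, when the section's own rate implies far fewer. Second, Section 6.2 sets a significance threshold for everything while leaving the factors, groups and number of tests open.

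With no control group, the listed tests can only compare subgroups within the cohort. Completion is both the primary endpoint and the stated basis for the optimal scenarios, so completers against non-completers is the natural split. If one of those groups is small and the list of characteristics is open, moderate true differences will often be missed, and those that reach p < 0.05 will tend to be too large or due to chance. The intended output is advice on when to select an airway technique, so a spurious predictor would matter.

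**Working it through.** **Reproducing 86.** The inputs in Section 6.1 are "For the confidence interval of 95% and the margin of error of 5% with the rate of 16" (per cent) and 144 qualifying cases a year.

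- Single-proportion precision: n0 = 1.96² × 0.16 × 0.84 / 0.05² = 206.5.
- Finite-population correction with 144: 206.5 / (1 + 205.5/144) = 85.1, rounded up to 86.

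The plan does not mention the correction, but the stated figure follows from it; without it the answer is 207. Either way the result is a number to enrol, not a number expected to complete.

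**Completers at the stated rate.** 0.16 × 86 = 13.8, and 0.16 × 100 = 16 (binomial 95% range 9 to 23).

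**Completers at the plan's own switch limit.** The 16% is the share of procedures shorter than 22.5 − 4.5 = 18 minutes. At 18 minutes the model gives 37.5 + 18 × 1.125 = 57.75 mmHg, already above 55 mmHg. The model starts from an end-tidal value and the limit applies to TcpCO2 less the baseline gradient, so the two are on the same scale.

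- Time to 55 mmHg: (55 − 37.5) / 1.125 = 15.56 minutes.
- z = (15.56 − 22.5) / 4.5 = −1.543, probability 6.1%.
- About 6 of 100 (binomial 95% range 2 to 11).

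**False positives.** The number of characteristics is not given, so it is assumed here. For m independent null factors at 0.05, the chance of at least one false positive is 1 − 0.95^m: 23% for 5 and 40% for 10.

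**Power and exaggeration.** Assumed: a two-sided t-test at 0.05 and a true difference of 0.3 SD. The standard error in SD units is √(1/n1 + 1/n2), and the difference needing 80% power is about 2.80 times that. For 16 versus 84: √(1/16 + 1/84) = 0.273, × 2.80 = 0.76; the noncentral t gives 0.77. Overstatement is the mean absolute difference among significant results divided by the true difference, by simulation.

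| Split | SE (SD) | Difference for 80% power | Power at 0.3 SD | Overstatement when significant |
|---|---|---|---|---|
| 16 vs 84 | 0.273 | 0.77 SD | 19% | 2.3-fold |
| 6 vs 94 | 0.421 | 1.19 SD | 11% | 3.4-fold |
| 50 vs 50 | 0.200 | 0.57 SD | 32% | 1.7-fold |

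Taking Section 6.1 literally, 86 completers against 14 others, 80% power needs 0.82 SD.

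**The case against.** The strongest reply is that this is a single-arm pilot that sets out to describe. Section 6.3.2 aims only at averages and standard deviations, no section writes down a comparison of completers with non-completers, and leaving secondary work to be settled with a statistician is ordinary wording. This stands in part: the comparison is an inference from Sections 2, 3.1 and 6.2. But a descriptive aim does not fit a significance threshold applied to all analyses, and that threshold is the real weakness in Section 6.2.

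Three stronger readings are tempting and are not supported.

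- *That the comparison will rest on 16, or 6, completers.* Both come from an apnoea model with a mean of 22.5 minutes. Section 3.3 expects most cases to be done within 20 minutes, where that model puts only 29% (z = (20 − 22.5)/4.5 = −0.556). It also plans no muscle relaxation, and Section 2.1 includes spontaneously breathing patients. Completion could therefore be higher. How much higher cannot be computed: at 20 minutes the same rate of rise gives 37.5 + 20 × 1.125 = 60 mmHg, and the documents do not say how many cases will finish before 15.56 minutes or how CO2 rises in breathing patients.
- *That having 16 completers instead of 86 causes the power problem.* The smaller group governs. 86 versus 14 needs 0.82 SD and 16 versus 84 needs 0.77 SD, nearly the same. The 86 sentence is wrong, but correcting it does not change the precision.
- *That false predictors are certain.* With ten independent null factors there is still a 60% chance of none. Section 3.3 names only five characteristics, and BMI is computed from two of the others, so independence is only approximate. A true difference of 0.8 SD has 83% power at 16 versus 84.

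**Conclusion.** The concern holds in a limited form. From the documents alone: 86 is mislabelled; the plan's own inputs imply about 14 completers of 86 (16 of 100), or about 6 of 100 at its 55 mmHg limit; the 16% and that limit disagree and must be reconciled; and Section 6.2 sets p < 0.05 for every analysis with no named factors and no multiplicity control.

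The consequence is a high risk, not a certainty, that an ideal-patient comparison gives chance or overstated findings. Its size depends on assumptions that the plan does not supply: the number of factors (5 to 10 here), their independence, the 0.3 SD effect and the completion split. An even split eases the power problem but does not remove it (32% power, 1.7-fold overstatement), and the false-positive calculation does not depend on the split. This is a point that should be changed; it does not undermine the primary endpoint.

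**What to change.** In Section 6.1, restate 86 as the total to enrol and give the expected number of completers beside it, after reconciling the 16% with the 55 mmHg limit. Say that the expectation rests on the apnoea model, and how it sits with the 20-minute expectation in Section 3.3.

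In Section 6.2, name before enrolment a short list of characteristics for the completion comparison. How short is a judgement; the fewer the completers, the shorter it should be. Report completion rates or differences with 95% confidence intervals, label them exploratory, and make no significance claims for other characteristics.

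The cost is protocol wording, with no extra patients or procedures. The downside is fewer statistically significant statements in the report.

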## **6.3 Control of Bias and Confounding**

This is an interventional study that will involve recruitment of subjects who are scheduled to undergo an upper airway surgery and are good candidates for use of Hi-VNI during their procedure. The investigators for this study expect some degree of bias during the subject recruitment phase, but this selection bias will help exclude patients who will not tolerate use of Hi-VNI for oxygenation during surgery due to their co-morbidities. Please see Section 4.4 for exclusion criteria defined for this study.

CONFIDENTIAL

This material is the property of the University of Pennsylvania.

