## **3 Investigational Plan**

### **3.1 General Design**

This is a prospective, interventional, pilot study that will describe the select cases of upper aerodigestive tract surgery performed at our institution with use of the Hi-VNI device. Data captured will be analyzed with a goal of determining the efficacy of this oxygenation technique for upper airway surgery. We will also collect useful clinical information about the most optimal clinical scenarios for use of this technique based on the cases in our data sample that will demonstrate successful case completion without a need for adjunct oxygenation techniques aside from Hi-VNI such as jet ventilation or endotracheal intubation.

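### Section 6.3 presents selection bias as a help, selection rests partly on undocumented judgement, and no consecutive approach or log is described, so the single-arm completion rate can be biased upward by an amount that depends on caseload

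*Combined protocol and SAP*

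**What the plan says.** Section 6.3 describes the recruits as patients well suited to Hi-VNI, expects some bias in recruitment, and says that "this selection bias will help exclude patients who will not tolerate use of Hi-VNI for oxygenation during surgery due to their co-morbidities". It then refers to the exclusion list in Section 4.4. It names no measure to limit or document the bias. Section 3.1 says the study "will describe the select cases of upper aerodigestive tract surgery performed at our institution".

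Other sections add judgement to the fixed list:

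- Section 5.1: the principal investigator identifies eligible patients from the surgical or clinic schedule. No order of approach is given.
- Section 10.3: surgeon and anesthesiologist jointly assess each subject before enrolment.
- Section 5.4: the investigators may discontinue a subject they judge unsuitable, just before or during the operation. Section 5.4.1 requires no additional follow-up data on withdrawn subjects.
- Section 8.2: study numbers go to qualified patients. No record of the others is mentioned.

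The primary endpoint (3.4.1) is the proportion of cases completed on Hi-VNI alone. There is no control group (6.1). On caseload, Section 6.1 says "there are 2-3 elective cases per week performed by the PIs that may qualify", and then "If 3 cases per week is used will equal to 144 qualified cases per year". From this, "the calculated sample size will equal to 86 individuals", and "we added 14 patients to the sample size" to reach 100.

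**The concern.** In a single-arm study of a proportion, the cases that enter determine the result. Applying a fixed exclusion list narrows the population but does not distort the rate among eligible patients. Unrecorded judgement about who will do well can distort it. Here the people who choose cases also deliver the technique and decide when to abandon it. Section 6.1 ties completion to procedure length, which a surgeon can partly foresee, so selection related to outcome is plausible.

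Without counts of eligible cases passed over or removed, a reader could not tell whether the rate describes eligible upper airway surgery at this centre or a favourable part of it. The objective of describing suitable patients and scenarios (Section 2) would rest on a narrowed range of cases, to an unknown degree.

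**Working it through.** **1. The plan's sample size.** Inputs from Section 6.1: 95% confidence, margin e = 0.05, rate p = 0.16, pool N = 144 (3 per week, hence 144/3 = 48 weeks).

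- Simple formula: n0 = 1.96² × 0.16 × 0.84 / 0.05² = 206.5, so 207. This is not 86.
- With finite-population correction: n = 206.5 / (1 + 205.5/144) = 85.1, so 86. This matches.

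The correction is valid only if the enrolled are a random sample of the 144. Without it, the margin at n = 86 is 1.96 × √(0.16 × 0.84/86) = 7.7 points; with it, 4.9 points.

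**2. Largest bias from choosing cases.** If every completer is among the 100 enrolled, the observed rate is p × N/100. At p = 0.16:

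| Cases per week (48 weeks) | N | Left out | Highest observed rate | Ceiling on bias |
|---|---|---|---|---|
| 2 | 96 | 0 | 16.0% | 0 |
| 2.5 | 120 | 20 | 19.2% | +3.2 points |
| 3 | 144 | 44 | 23.0% | +7.0 points |

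Passing 5 points needs 0.16 × N/100 > 0.21, that is N > 131.25, so at least 132 qualifying cases.

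**3. How strong the sorting must be at N = 144.** The bias equals the share left out times the gap in completion between enrolled and left-out cases. The share is 44/144 = 30.6%, so 5 points needs a gap of 0.05/0.306 = 16.4 points. In whole cases, 16% of 144 is 23 completers, and 21/100 enrolled against 2/44 left out gives 21.0% against 23/144 = 16.0%. Random sampling would put 21 or more of the 23 among the 100 with probability about 0.9% (hypergeometric).

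**4. Partial sorting.** Assume duration is normal with mean 22.5 and SD 4.5 min (Section 6.1), completion means under 18 min (15.9%), and the 100 cases with the shortest predicted duration are enrolled. The correlation between predicted and actual duration is an assumption, shown as a range:

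| Correlation | N = 144 | N = 120 |
|---|---|---|
| 0.3 | 19.2% (+3.3 to +3.4) | 17.7% (+1.8 to +1.9) |
| 0.5 | about 21% (about +5) | 18.5% (+2.6 to +2.7) |
| 0.7 | 22.4% (+6.5) | 19.0% (+3.1) |

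**5. The rate implied by the 55 mmHg limit.** Section 6.1 starts at 37.5 mmHg and rises by 1.125 mmHg/min, so 55 is reached at (55 − 37.5)/1.125 = 15.6 min. The normal model puts 6.1% of cases below that. The ceiling at N = 144 is 6.14% × 1.44 = 8.8%, or +2.7 points.

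**6. Removal after enrolment.** This route does not depend on caseload. If 16 of 100 complete and 24 non-completers were removed and left out of the denominator, the rate would be 16/76 = 21.1% (+5.1 points). The number 24 is illustrative. The documents do not say how many removals are expected or whether removed subjects stay in the denominator.

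**The case against.** The strongest reply is that the quoted sentence concerns co-morbidities and points straight to Section 4.4, and that Section 10.1 describes patients who are not candidates mainly by those same conditions. On that reading Section 6.3 only restates fixed criteria. This is fair to the sentence taken alone. It does not remove the judgement allowed in Sections 5.1, 5.4 and 10.3, which no log would make visible.

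A second reply is that this is a single-centre pilot that openly describes selected cases, and that some of the 44 left out would be patients who declined consent, which Section 6.1 anticipates. That also stands: the 44 are not all investigators' choices, and the ceilings above are upper limits.

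Three stronger readings are tempting, and the documents do not support them:

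- That the bias will exceed the plan's 5-point margin. This needs the top of the stated caseload range together with strong sorting, or substantial removal after enrolment.
- That investigators will pick short or easy cases. No section says so; step 4 is a what-if.
- That no record will be kept. The documents describe none, but the content of the schedule of events is not in the text available.

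Nor does selection make the search for suitable patients circular. Section 3.1 looks within the sample at cases completed without adjuncts, so selection narrows the range studied.

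**Conclusion.** The point stands as a cheap improvement. The plan expects selection bias, presents it as useful, allows judgement beyond Section 4.4 before and after enrolment, and describes no consecutive approach or log. Its precision calculation nevertheless depends on random sampling from 144 cases. An upward bias in the completion rate is possible, and as the plan is written a reader could not assess it.

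Its size is conditional. At 16% with 100 enrolled, choice of cases can add at most 7.0 points at 144 qualifying cases, 3.2 at 120 and nothing at 96. An assumed correlation of 0.5 gives about 5 points at 144 and under 3 at 120. At the 6.1% rate the ceiling is 2.7 points. A general claim that the 5-point margin is exceeded would go too far.

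**What to change.** In Sections 3.1, 4.5, 5.1 and 6.3:

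- Approach every patient who meets Sections 4.3 and 4.4 in schedule order.
- Log each eligible case not enrolled, and each subject removed after consent, with reason, pathology site and planned procedure.
- Report enrolled over eligible beside the completion rate, and compare enrolled with non-enrolled cases on the logged features.
- Keep every case started on Hi-VNI in the denominator of the primary endpoint, including subjects removed later.
- Replace the sentence that presents selection bias as a help with a statement that the fixed criteria of Section 4.4 define the population and that any further selection is recorded and reported as a limitation.

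Clinicians remain as free as now to decline or stop a case; the decision is simply recorded. The cost is a short log entry for about one case per week or fewer (44 cases over 48 weeks at the upper caseload), and possibly a lower reported rate.
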